### ***Risks related to memantine administration***

Memantine can cause a variety of side effects that can range from mild to severe and serious (see [Section 1.2.2](#)). Many of these have been reported from clinical trials in patients with AD, i.e. in patients with considerable comorbidities.

Data from clinical trials with memantine administration in healthy volunteers indicate good tolerability in general. Dizziness, headache, somnolence, decreased appetite were observed adverse events and increased ALT values were seen in the safety lab. These AEs were mild to moderate, they are monitorable and will be reflected in the safety measures.

### ***Risks related to the combined administration of BI 425809 and Memantine***

Based on available data (see [Section 1.2](#)), a clinically relevant pharmacokinetic or pharmacodynamic interaction between memantine and BI 425809 is considered unlikely based on the following considerations:

#### ***Pharmacokinetic interaction:***

Memantine selectively inhibits CYP2B6 activity at clinically relevant concentrations, whereas inhibition of other CYPs during memantine therapy is unlikely, i.e. it is not expected to affect BI 425809 metabolism that is mostly CYP3A4 mediated (see [Section 1.2.1.1](#)) [[P04-11747](#)]. In vitro memantine also inhibits OCT2 and to a lesser extent MATE. BI 425809 is not a substrate of OCT2, regarding MATE there are no in vitro data available. However, as the gMean fractional renal excretion of BI 425809 is low (around 5% over all dose groups), the impact of a potential interaction via MATE inhibition should be minor (see [Section 1.2.1.1](#)).

Proprietary confidential information © 2019 Boehringer Ingelheim International GmbH or one or more of its affiliated companies

For memantine, no cytochrome P450-catalysed metabolism has been detected in vitro. An interaction based on the mild induction potential of BI 425809 on CYP3A4 is therefore considered unlikely. The renal transporters OCT2 and MATE1 may be involved in the tubular secretion of memantine [[R17-3276](#)]. In in vitro studies, BI 425809 did not inhibit the organic cation transporter OCT2 and was found to only inhibit MATE1 and MATE2K transporters with IC50 values between 30 and 100 uM [[n00241265](#), [n00263124](#)]. Based on exposures associated with the current highest dose of BI 425809 (25 mg qd) and DDI prediction approaches outlined in regulatory guidelines [[P14-08681](#), [P12-05791](#)], clinically-relevant inhibition of memantine renal secretion is considered unlikely. No trend towards an alkalization of urine by BI 425809 has been observed after multiple doses of BI 425809 (CTR 1346.2, Listing 1.1 [[c02958024](#)]).

Pharmacodynamic interaction:

Both drugs, BI 425809 and memantine, are targeting the NMDA receptor (NMDAR). However, the mode of action of both drugs is different.

Memantine is a moderate-affinity uncompetitive NMDAR antagonist. The NMDAR is a voltage-sensitive, glutamate-gated ion channel that, after activation, allows entry of calcium into the neuron. One hypothesis is that chronic overactivity at the NMDAR, allows excessive calcium influx and may via subsequent synaptic or dendritic damage, necrosis or apoptosis, play a role in the progression of AD, especially at later stages of the disease (moderate-to-severe). At rest, the NMDAR channel is blocked by a magnesium ion. Memantine binds at, or near, the magnesium-binding site and thereby blocks calcium entry into the cell at times of partial neuronal depolarization, but allows entry during full neuronal depolarization. This allows normal physiologic signal transmission during times of learning or recall, along with inhibiting pathologic, tonic overactivation [[P18-12042](#), [R18-3925](#)].

BI 425809 inhibits GlyT1 leading to increased glycine concentrations in the synaptic cleft. Glycine is a physiological co-activator of the NMDAR. The physiological NMDAR function is critical for learning and memory and cognitive performance. It has been shown that mice with point mutations in the NMDAR glycine binding site display greatly reduced NMDAR function and show severe deficits in learning and memory performance. These deficits can be rescued by administration of the NMDA receptor glycine site agonist D-serine [[R18-3925](#)].

BI 425809 is hypothesized to reduce NMDAR hypofunction in regard to disturbed physiological signal transmission required for learning and memory. On the other hand memantine is thought to inhibit the overactivation of the NMDAR in late stage Alzheimer's disease patients, while at the same time it does not affect at therapeutic exposure levels (approximately 50% occupancy of the NMDAR) the physiological signal transmission needed for cognitive function.

Therefore, in conclusion, a pharmacodynamic interaction of BI 425809 and memantine by counteracting the effects of the other drug is not expected.

Proprietary confidential information © 2019 Boehringer Ingelheim International GmbH or one or more of its affiliated companies

### ***Drug-induced liver injury***

Although rare, a potential for drug-induced liver injury (DILI) is under constant surveillance by sponsors and regulators. Therefore, this trial requires timely detection, evaluation, and follow-up of laboratory alterations in selected liver laboratory parameters to ensure subjects' safety; see also [Section 5.2.8.1.4](#), adverse events of special interest.

#### ***Safety measures:***

- A thorough screening examination will ensure that only suitable healthy subjects will enter the study, for example subjects with
  - with high liver enzymes or history of or current liver disease
  - GFR < 80 ml/min
  - medical conditions or nutrition habits that may cause urine alkalizationwill be excluded from study participation.
- Close monitoring of
  - Adverse events
  - Safety lab (special focus on hepatic parameters, eGFR)
  - ECG and Vital signs (focus on blood pressure)
  - C-SSRS
- Prohibition to use drugs that may cause urine alkalization ([Section 4.2.2](#))
- Drugs, medical conditions or nutrition habits that may cause urine alkalization are not allowed
- As memantine may impact the ability to operate vehicles and/or machines, subjects are not allowed to drive a vehicle or operate machines during Visit 3 and 4
- Close medical surveillance for at least 25 hours post-dose on the day of first administration of BI 425809 and memantine, respectively, and for up to 49 hours post-dose after combined administration of BI 425809 and memantine

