## FLOW CHART

Period	Visit	Day	Planned time (relative to first drug administration) [h:min]	Approximate clock time of actual day [h:min]	Event and comment	Safety laboratory	Safety assessments	PK BI 425809 blood	PK memantine blood	PK urine memantine	C-SSRS	Vital signs (BP, PR) & 12-lead ECG	Questioning for AEs and concomitant therapy 
SCR	1	-21 to -1			Screening (SCR) 	x	x 				x	x	
1 	2	2	-1	-14:00	18:00	Admission to trial site	x 	x 			x		x
		1	1	-2:00	06:00	Allocation to subject numbers 	x 		x 	x 		x 	x 
				0:00	08:00	Administration of 25 mg BI 425809							
				0:30	08:30				x				
				1:00	9:00				x				
				2:00	10:00	240 mL fluid intake			x				
				3:00	11:00				x				
				3:30	11:30				x				
				4:00	12:00	240 mL fluid intake, thereafter lunch 			x			x	x
				4:30	12:30				x				
				5:00	13:00				x				
				6:00	14:00				x				
				7:00	15:00				x				
				8:00	16:00	Snack (voluntary)			x				
				10:00	18:00				x				
				11:00	19:00	Dinner 						x	x
				12:00	20:00				x				
		2	24:00	08:00	Administration of 25 mg BI 425809	x		x 					x
			25:00	09:00	Breakfast (voluntary), discharge from trial site						x	x	
		3	48:00	08:00	Ambulatory visit, Administration of 25 mg BI 425809							x	
		4	72:00	08:00	Ambulatory visit, Administration of 25 mg BI 425809							x	
		5	96:00	08:00	Ambulatory visit, Administration of 25 mg BI 425809	x						x	
		6	120:00	08:00	Ambulatory visit, Administration of 25 mg BI 425809							x	
		7	144:00	08:00	Ambulatory visit, Administration of 25 mg BI 425809							x	
		8	168:00	08:00	Ambulatory visit, Administration of 25 mg BI 425809							x	

Proprietary confidential information © 2019 Boehringer Ingelheim International GmbH or one or more of its affiliated companies

Period	Visit	Day	Planned time (relative to first drug administration) [h:min]	Approximate clock time of actual day [h:min]	Event and comment	Safety laboratory	Safety assessments	PK_BI 425809 blood	PK_memantine blood	PK_urine memantine	C-SSRS	Vital signs (BP, PR) & 12-lead ECG	Questioning for AEs and concomitant therapy 
2 	3 	9	192:00	08:00	Ambulatory visit, Administration of 25 mg BI 425809	x					x		x
			202:00	18:00	Admission to trial site	x 	x 			x		x	

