#### 1.2.1.3 Clinical experience in humans

At the time of preparation of this clinical trial protocol, BI 425809 has been investigated in eight Phase 1 trials. Two Phase 2 trials (1346-0009 and 1346-0023) and one Phase 1 trial (1346-0015) are ongoing.

More than 245 healthy subjects have received one or more doses of BI 425809 (single doses of 0.5 mg to 150 mg and multiple doses of 5 mg to 75 mg bid (150 mg/day)), including 18 subjects aged 65 years or older (for details please refer to IB, Table 6.1:1 [[c02155957](#)]). Altogether, BI 425809 was generally well tolerated in young and elderly healthy male and female volunteers. No deaths or serious adverse events (SAEs) and no AEs of special interest (AESI) were reported. Across all BI 425809 treatment groups, there were 3 subjects with severe, but self-limiting AEs. Overall, drug-related AEs have been seen more frequently in the subjects treated with BI 425809 (33.5% vs 26.9% on placebo). Across all BI 425809 treatment groups, 3 subjects discontinued treatment due to an AE (2x nausea and vomiting, 1x procedural headache), all subjects recovered (for details please refer to IB, Table 6.3.1.1:3 [[c02155957](#)]).

The most frequent AEs for BI 425809 were nervous system disorders (25.3%), with headache being the most common (18.0%). These AEs appear to be dose-related, with a tendency for greater frequency at higher doses and can be clinically monitored.

In addition, transient visual disturbances (at doses  $\geq$  25 mg BI 425809 qd, mainly blurred vision) and somnolence (drowsiness) were observed. These effects are mostly mild to moderate and transient.

In general, there were no clinically relevant findings in the clinical laboratory evaluation, 12-lead ECG, vital signs. No suicidal ideation or behaviour was observed. No notable decrease in haemoglobin or haematocrit was noted in the BI 425809 treatment groups compared with placebo.

For a more detailed list of observed AEs and safety measures please refer to the current Investigator's Brochure, section 6 [[c02155957](#)].

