#### 1.2.1.4 Clinical pharmacokinetics

After administration of BI 425809 tablets, maximum plasma concentrations of BI 425809 occurred around 3 to 5 h after dosing. The terminal half-life was independent of the administered dose and ranged from 37 to 59h. Exposure increased in the tested dose range of 5 to 75 mg but with a trend to a less than dose proportional behaviour for doses of 50 mg and above. Food increased drug exposure (fed/fast ratio for  $C_{max}$ : 142%, for  $AUC_{0-tz}$ : 126%).

Steady state was reached after 6 days of BI 425809 dosing with accumulation ratios for  $C_{max}$  ranging from 1.96 to 2.63 and for AUC from 2.31 to 3.21. No exposure difference between

Proprietary confidential information © 2019 Boehringer Ingelheim International GmbH or one or more of its affiliated companies

young and elderly healthy subjects was observed. Furthermore, pharmacokinetics in Japanese and Chinese subjects were comparable with Caucasians.

As BI 425809 is a substrate of CYP3A4, co-administration of weak, moderate and strong CYP3A4 inhibitors and inducers is not permitted.

Due to a mild induction potential for CYP3A4 [[c08949593](#)], BI 425809 should be administered with caution in presence of sensitive substrates of these enzymes, and sensitive CYP3A4 substrates with a narrow therapeutic index are not permitted. BI 425809 had no relevant effect on CYP2C9, CYP2C19, and P-gp substrates.

In plasma from young and elderly healthy volunteers administered single or multiple oral doses of BI 425809 (10, 25 and 50 mg) (trials 1346.1 and 1346.2), four oxidative metabolites, M526, M528, BI 758790, and M544 and two metabolites resulting from hydrolysis of the amide bond, BI 761036 and M312 (IN00079211), were identified. BI 761036 was with 54% the main contributor to plasma drug-related exposure, BI 758790 occurs at plasma exposures similar to parent, each made up around 20% of total drug-related exposure.

For a more detailed description of the BI 425809 profile please refer to the current Investigator's Brochure [[c02155957](#)].

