Uncommon side effects of memantine include fungal infection, confusion, hallucinations (mainly observed in patients with severe Alzheimer's disease), abnormal gait, venous thrombosis/thromboembolism, vomiting, fatigue and cardiac failure.

Seizures are described as very rare side effects.

From post-marketing experience there were reports of psychotic reactions, pancreatitis, and hepatitis in the context of memantine use. The frequency of these events is not known. Further In post-marketing experience depression, suicidal ideation and suicide have been reported in patients treated with Memantine. However, Alzheimer's disease has been associated with these events, too.

Memantine has minor or moderate influence on the ability to drive and use machines such that subjects should be warned to take special care.

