### Drug-related risks and safety measures

#### *Risks related to BI 425809 administration*

Proprietary confidential information © 2019 Boehringer Ingelheim International GmbH or one or more of its affiliated companies

In this trial, a dose of 25 mg BI 425809 q.d. will be administered over two periods of 10 days each, once alone and once in combination with memantine. Multiple oral doses of 25 mg BI 425809 have already been administered in trial 1346.2 (12 days) and 1346.3 (14 days) and are considered safe and well tolerated (for details please refer to [Section 1.2.1.3](#)). Further, two Phase II trials, one in patients with Alzheimer's disease (1346.23) and one in patients with CIAS (1346.9), are currently ongoing in which patients receive up to 25 mg BI 425809 qd in an ambulatory setting over a period of 12 weeks with no safety issues reported so far.

Based on its mechanism of action, its preclinical profile and the data obtained from ongoing and completed Phase I/II studies so far, there is no indication that BI 425809 should be regarded as a high risk compound.

The main dose-limiting AEs observed so far, were expected based on its mode of action. These adverse CNS symptoms, including dizziness, headache, and visual effects showed a trend towards dose dependency and were monitorable and reversible after treatment discontinuation. The reported adverse events were mostly of mild to moderate intensity and did not jeopardize the subject's wellbeing. Adequate safety monitoring including neurological examinations, vital signs/ECG, visual tests, safety laboratory, suicidality assessment and adverse events monitoring has been implemented. Though the trial is designed in parts in an ambulatory fashion, if the investigator has any clinical concern the safety of the subject will be paramount and the inpatient stay will be extended or initiated.

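### The ban on driving and operating machines omits Visit 2, where 8 of 10 doses of BI 425809 25 mg peak outside the unit at a dose with reported blurred vision

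*Protocol*

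**What the plan says.** The safety measures in Protocol Section 1.4 state that "subjects are not allowed to drive a vehicle or operate machines during Visit 3 and 4", and memantine's possible effect on these activities is the only reason given. The one other mention of driving, in Section 1.2.2.2, is also about memantine: "Memantine has minor or moderate influence on the ability to drive and use machines such that subjects should be warned to take special care". The restrictions in Sections 4.2.2.1 and 4.2.2.2 contain no driving rule.

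On BI 425809, Section 1.2.1.3 describes transient visual disturbances at 25 mg once daily and above, and continues: "mainly blurred vision) and somnolence (drowsiness) were observed. These effects are mostly mild to moderate and transient". Section 1.4 returns to the main dose-limiting events: "These adverse CNS symptoms, including dizziness, headache, and visual effects showed a trend towards dose dependency".

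Visit 2 gives 25 mg once daily on Days 1 to 10. The Flow Chart entry for 25:00, one hour after the Day 2 dose, is "Breakfast (voluntary), discharge from trial site". From Day 3 to Day 9 each dose is listed as "Ambulatory visit, Administration of 25 mg BI 425809", with readmission at 202:00 on Day 9. Section 6.2.2 requires a fitness check before each discharge.

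**The concern.** The plan treats one of the two drugs as a driving hazard and is silent on the other, although its own account of the second drug includes blurred vision from exactly the dose used. A subject who follows the protocol to the letter may drive or operate machinery through the BI 425809 peak on most days of Visit 2.

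The plan also applies an uneven standard. For memantine, a source statement that asks only for a warning became a full ban, which runs from the first 5 mg dose of titration. For BI 425809, blurred vision, somnolence and dizziness led to neither a ban nor a caution in the text available, and no reason for the difference is given. These are healthy volunteers with no therapeutic benefit, so a cheap precaution is worth having even where the risk is modest. The matter concerns subject safety only and touches no endpoint, estimate or sample-size figure.

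**Working it through.** The plan gives no figure to reproduce. The check is a count from the Flow Chart.

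**Inputs**
- Visit 2 dose times: 0, 24, ..., 216 h, ten doses (Flow Chart; Section 4.1.1).
- Time in the unit: from 14 h before the first dose to 25 h, and from 202 h to 240 h (Flow Chart). Section 6.2.2 gives 24 h as the minimum for the first stay, so 24 h was tried as well.
- Time to peak (Section 1.2.1.4): "maximum plasma concentrations of BI 425809 occurred around 3 to 5 h after dosing".
- Accumulation (Section 1.2.1.4): "Steady state was reached after 6 days of BI 425809 dosing with accumulation ratios for" Cmax of 1.96 to 2.63.
- Planned subjects: 16.

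**Where each dose peaks** (peak time = dose time + 3 to 5 h)

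| Day | Dose (h) | Peak (h) | Location at peak |
|---|---|---|---|
| 1 | 0 | 3–5 | in the unit |
| 2 | 24 | 27–29 | outside, 2–4 h after discharge at 25 h |
| 3–8 | 48–168 | 51–173 | outside |
| 9 | 192 | 195–197 | outside, 5–7 h before readmission at 202 h |
| 10 | 216 | 219–221 | in the unit |

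Days 2 to 9 peak outside, which is 8 of 10 doses. The count stays at 8 for a peak at 3, 4 or 5 h and for discharge at 24 or 25 h.

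**Size**
- Subject-doses peaking outside: 8 × 16 = 128.
- Outpatient window: 202 − 25 = 177 h; 177 / 24 ≈ 7.4 days.
- Steady state after 6 days means that the Day 7, 8 and 9 doses peak outside at steady state: 3 × 16 = 48 subject-doses, with Cmax about 1.96 to 2.63 times the first-dose value.
- Cross-check: with the stated half-life of 37 to 59 h and simple first-order accumulation, the fraction of steady state is 1 − exp(−ln 2 × 24n / half-life). For n = 7 this is 0.96 (37 h) and 0.86 (59 h); for n = 9 it is 0.98 and 0.92. Days 7 to 9 are therefore at or near steady state across the stated range.

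**Do existing safeguards cover these days?**
- The fitness check happens at discharge. On Day 2 that is 2 to 4 h before the peak.
- Visual tests carry Flow Chart footnote 17, which appears only at screening, at Day −1 of Visit 2 and at the end of trial. None falls on an outpatient day of Visit 2.
- Unscheduled visual tests (Section 5.2.3) need a reported visual symptom or the investigator's judgement. Unscheduled neurological examinations (Section 5.2.1) follow reported CNS events.
- The 25 h of surveillance after the first dose covers only the lowest of the ten peaks.

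**The case against.** The strongest reply is that the facts are right but carry little weight. Section 1.4 says that 25 mg was given for 12 and 14 days in two earlier trials, longer than Visit 2, and was considered well tolerated. It also says that outpatient Phase II dosing up to 25 mg daily had raised no safety issue. The sponsor considered the outpatient design and allows the inpatient stay to be extended or started on clinical concern. Subjects come to the site for dosing on each of Days 3 to 9, and people notice blurred vision or drowsiness themselves. No document reviewed says that BI 425809 affects driving. The visual effects are reported over a range that starts at the trial dose and, with multiple dosing up to 150 mg a day, reaches well above it. Nothing links them to the time of peak, and the accumulation ratios are not specific to 25 mg. Finally, the investigator's brochure and the subject information may already carry advice.

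Much of this stands, and it lowers the urgency. The counts measure exposure, not events. The peak-timing argument is an assumption, but dropping it does not help the plan: with a half-life of 37 to 59 h, effects not tied to the peak could occur at any point in the 177 h outside the unit. Good tolerability does not settle the matter, because mild blurred vision that is acceptable in a clinic is not acceptable at the wheel. The documents do not say whether the Phase II trials restricted driving. Extending the stay, like the unscheduled tests, requires a concern to have arisen first. If unseen documents do contain a driving rule, the protocol should match them.

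**Conclusion.** The concern holds. The ban leaves out Visit 2, and nothing in the available text restricts driving there, although 8 of 10 doses (128 subject-doses) peak outside the unit at a dose for which the protocol itself reports blurred vision. Of these, 48 subject-doses fall on Days 7 to 9, at or near steady state.

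The conclusion assumes discharge and readmission as scheduled, all 16 subjects completing Visit 2, and the protocol's own time to peak. It does not show that harm is likely: no incidence at 25 mg is given, and somnolence and dizziness are reported without a dose. This is a recommended, low-cost safety improvement and not a flaw that undermines the trial.

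**What to change.** Rewrite the Section 1.4 bullet so that it names both drugs and all three treatment visits. Wording that claims no more than the protocol reports would be:

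*Because memantine may affect driving and the use of machines, and because visual disturbances, somnolence and dizziness have been reported with BI 425809, subjects must not drive or operate machines during Visits 2, 3 and 4.*

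Repeat the rule in Section 4.2.2.2, where the other lifestyle restrictions are listed, and in the subject information.

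The cost is a protocol amendment and revised subject information, with the approvals that Section 8.1 requires and possibly re-consent of subjects already enrolled. For subjects it adds about 9 outpatient days without driving (Days 2 to 9 and the Day 11 discharge day: 8 + 1 = 9), on top of the 35 + 10 = 45 dosing days already covered in Visits 3 and 4. Dosing, sampling, sample size and analysis do not change.

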## **2. TRIAL OBJECTIVES AND ENDPOINTS**

### **2.1 MAIN OBJECTIVES, PRIMARY AND SECONDARY ENDPOINTS**

#### **2.1.1 Main objectives**

To investigate the effect of steady state exposures of memantine on the steady-state pharmacokinetics of BI 425809 and vice versa in healthy subjects.

